## 7.2. Discussion of Study Design

This is a multicenter, randomized, double-blind, placebo-controlled Phase 3 study evaluating the efficacy and safety of HP-5000 in subjects with OA pain of the knees. Such a design is well accepted and considered standard in drug development when evaluating new therapeutic modalities across different disease areas.

A parallel-group design was selected because it is free of the assumptions underlying competing designs (for example, crossover). A parallel-group approach is considered the optimal study design to evaluate efficacy in pivotal registration clinical trials.

The use of a randomized double-blind design will minimize bias by randomly assigning the subjects to treatment arms, and ensuring that the subjects, investigators and site personnel, and the Sponsor/designee are blinded to the treatment allocations.

A placebo control will be used to allow for an unbiased assessment of treatment effects and safety data. The comparison with placebo is justified as subjects will be closely monitored and study treatment will be discontinued and the subject will be returned to standard of care (SOC) treatment if their status deteriorates.

The rationale for dose selection is described in [Section 9.6](#).

The 12-week duration is considered to be sufficient to evaluate the effect on chronic pain of OA. This time period is also sufficient to evaluate changes in the primary and secondary outcome measures.

The use of rescue medication is prohibited within 3 calendar days prior to the Baseline Visit, on the day of Baseline Visit (V3), from Baseline Visit until Visit 4, within 2 calendar days prior to all subsequent visits (V5, V6, V7, and V8), and on the day of the clinic visits (V4, V5, V6, V7, and V8), thus ensuring the integrity of the pain assessments and safeguarding against confounding due to rescue medications.

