### **8.2.3 Premature Subject Withdrawal**

All subjects are free to withdraw from participation in the study at any time, for any reason, specified or unspecified, and without prejudice to further treatment. The criteria for enrollment are to be followed explicitly and if a subject who does not meet enrollment criteria is inadvertently enrolled, that subject should be withdrawn from the study and the Sponsor or CRO must be notified.

Subjects should not be asked to withdraw from the study because of experiencing AE, lack of efficacy, pregnancy, or lack of compliance to the clinical study protocol, etc. Those patients can stop their study treatments (for subjects who do not comply the protocol specified instructions and procedures, every effort will be made to keep them in the study after stopping treatment unless there is an adverse impact on subject safety). Discontinuation from study treatment does not automatically lead to a complete withdrawal from the study. Subjects discontinuing from study treatment are strongly encouraged to continue in the study up to the study completion (Follow-up Phone Visit, Week 13).

Subjects who decide they do not wish to remain in the study should NOT be considered withdrawn from the study UNLESS they withdraw their consent. Subjects are encouraged to return to all scheduled site and telephone visits, perform all procedures (including eDiary completion and blood draws) and follow the all requirements of the protocol (including the prohibited therapies), but without study treatment administration, until the end of the study (Follow-up Phone Visit, Week 13).

The reason for study treatment discontinuation and withdrawal from the study will be separately recorded. When the subject discontinues study treatment and/or withdraw from the study, the reason will be recorded in the medical records and eCRF using the below categories for discontinuation of study treatment and withdrawal from the study respectively.

The reasons will be grouped into three main categories: “study treatment related”, “not study treatment related”, and “uncertain” and more specific sub-categories will be described under each of the three main categories.

- Study treatment related
  - Lack of efficacy
  - Adverse events
  - Deviation from protocol (Please specify the deviation)
  - Other
- Not study treatment related
  - Adverse events
  - Prohibited Medication Use
  - Pregnancy
  - Deviation from protocol (Please specify the deviation)
  - COVID-19

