### **11.2.4 Treatment of Adverse Events**

Adverse events that occur during the study will be treated, as necessary, by established standards of care. If such treatment constitutes a deviation from the protocol, the subject should be withdrawn from the study and the reason and date of withdrawal must be documented in the eCRF. The decision about whether the subject may continue in the study will be made by the sponsor after consultation with the investigator and/or Medical Monitor.

If a subject experiences an intolerable AE , the investigator must decide whether to withdraw the subject from the study and/or treat the subject. Special procedures may be recommended for the specific study drug, such as the collection of a serum sample for determining blood concentrations of study drug, or treatment regimens, as appropriate.

It is **NOT** necessary to unblind a subject’s treatment assignment in most circumstances, even if an SAE has occurred. If unblinding is necessary, see **Section 9.5** for a description of the unblinding procedures.

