### **11.2.7 Pregnancy Reporting**

All females of childbearing potential who participate in the study should be counseled on the need to practice adequate birth control and on the importance of avoiding pregnancy during study participation. Females should be instructed to contact the investigator or study staff immediately if pregnancy occurs or is suspected.

Male study participants will be instructed to practice birth control measures to prevent a partner's pregnancy during the subject's study participation and for 90 days following the last dose administration.

Pregnancy testing will be conducted prior to administration of study drug on every female of childbearing potential. A female who is found to be pregnant at the Screening Visit will be excluded from the study and considered to be a screening failure.

A female who becomes pregnant during study will immediately discontinue the study treatment. The subject is encouraged to return to all scheduled site and telephone visits, perform all procedures (including eDiary completion and blood draws) and follow the all requirements of the protocol (including the prohibited therapies), but without study treatment administration, until the end of the study (Follow-up Phone Visit, Week 13). Any female who becomes pregnant during treatment and within 30 days of discontinuing study drug will be followed by the investigator after the completion of the study until birth or termination of pregnancy. Any pregnancy for which the estimated date of conception occurred prior to the Termination Visit of the study and for 30 days following study drug discontinuation, whichever is longer, must be reported.

If an adverse outcome of a pregnancy is suspected to be related to study drug exposure, this should be reported regardless of the length of time that has passed since the exposure to study treatment.

An induced abortion or a spontaneous abortion is considered to be a SAE and should be reported in the same timeframe and in the same manner as all other SAEs (see [Section 11.2.6.1](#)).

The investigator must report the pregnancy to Noven using the **Noven Pregnancy Notification Report form** via the same email address as for SAE reporting. The investigator should contact the designated individuals who receive SAE notification and record information related to the pregnancy on a **Noven Pregnancy Notification Report form** provided by the sponsor or its designee.

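### Protocol 11.2.4 was left behind by the amended 8.2.3 and still points to study withdrawal, and the reason code for a patch stop after NSAID use for target-knee pain is ambiguous (minor)

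*Protocol*

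**What the plan says.** **Retention.** Protocol 8.2.3 states: "Subjects should not be asked to withdraw from the study because of experiencing AE, lack of efficacy". Pregnancy and non-compliance are named in the same sentence. A subject who does not wish to remain "should NOT be considered withdrawn from the study UNLESS they withdraw their consent". Those who stop the patch are encouraged to keep all visits and to "follow the all requirements of the protocol (including the prohibited therapies), but without study treatment administration, until the end of the study". For non-compliant subjects, the effort to retain them yields where staying would harm their safety.

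**Treatment of adverse events.** Protocol 11.2.4 says: "If such treatment constitutes a deviation from the protocol, the subject should be withdrawn from the study". Its next sentence gives the decision on continuation to the sponsor, after consultation.

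**Pregnancy.** Protocol 11.2.7 says: "A female who becomes pregnant during study will immediately discontinue the study treatment". It then keeps the subject in follow-up, as 8.2.3 does.

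**Reason codes.** Protocol 8.2.3 has reasons recorded "using the below categories for discontinuation of study treatment and withdrawal from the study respectively", so one list serves both decisions. "Prohibited Medication Use" appears only in the group not related to study treatment. Lack of efficacy appears only in the related group. Deviation from protocol appears in both.

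**Analysis.** Protocol 13.4.3.1 and SAP 16.1.4 apply zero benefit to treatment stops for related reasons. They leave out WOMAC pain scores taken after the patch has been off for more than 24 hours. SAP 16.1.2 assumes that missing scores are missing at random (MAR). SAP 16.1.5 gives non-compliance and protocol deviation as examples of related reasons.

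**Care.** Protocol 7.2 justifies placebo by saying that "study treatment will be discontinued and the subject will be returned to standard of care (SOC) treatment if their status deteriorates". Under 9.11 the NSAID ban lasts until study completion or early termination. The note to Visit 8 lets standard care resume after that visit.

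**The concern.** Two instructions to sites pull apart. A site that follows 11.2.4 may withdraw a subject whom 8.2.3 wants kept, and the later visits are lost. The situation is foreseeable in a patch trial. Skin irritation at the knee is recorded as an adverse event, and Table 2 bars topical corticosteroids on the knee and sedating antihistamines, so ordinary treatment of that irritation can be a deviation.

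The second matter is the reason code. The zero-benefit rule depends on whether a stop is classed as related to study treatment. If knee pain drives a subject to an NSAID and the patch is then stopped, more than one entry in 8.2.3 fits, and the entries fall on different sides of that split. The handling in the primary analysis would then depend on a choice made at the site without a written rule.

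**Working it through.** **Step 1: 11.2.4 against 8.2.3 and 11.2.7.** For an adverse event whose treatment deviates from the protocol, 11.2.4 makes withdrawal from the study the default, subject to the sponsor's decision. For an adverse event or non-compliance, 8.2.3 makes staying in the study the default, with the patch stopped. For pregnancy, 11.2.7 follows 8.2.3. The superseded protocol text in the same file has the same 11.2.4, next to an 8.2.3 that allowed withdrawal when a prohibited medication was needed. The amendment rewrote 8.2.3 and the pregnancy rule and left 11.2.4 unchanged. No text explains the difference.

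**Step 2: what retention gains.** A retained off-patch subject supplies safety data. The subject also supplies scores for the supplementary analysis (SAP 16.1.6) and the other secondary analyses (SAP 16.3), which make no adjustment for intercurrent events. If scores more than 24 hours off patch are excluded under SAP 16.1.4, the primary analysis does not gain.

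**Step 3: the codes open to one event.** For a patch stop after NSAID use for target-knee pain:

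- Lack of efficacy, or deviation from protocol in the related group: zero benefit from the stop.
- Prohibited medication use, or deviation from protocol in the unrelated group: the zero-benefit rule does not apply by that code. Off-patch scores are plausibly dropped and the MMRM treats the gap as MAR. The protocol's sensitivity rule also takes unrelated reasons as MAR. Of the SAP's three dropout patterns, the one that treats every dropout as missing not at random reaches such a subject. Table B also assigns both sensitivity methods to patch removal, and the SAP does not reconcile the table with the three patterns.

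**Step 4: size.** The plan has no figure to reproduce here; the effect size and sample size are redacted. All inputs below are assumptions.

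*Conditional prediction.* Take an arm mean change of -4 at the last observed visit and -5 at Week 12, a subject whose last change is 0, equal SDs, between-visit correlation ρ of 0.4 to 0.8, and zero benefit read as a change of 0.

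- MAR prediction = -5 + ρ × (0 - (-4)). At ρ = 0.4 this is -3.4; at ρ = 0.8 it is -1.8.
- Each 1% of an arm coded this way moves that arm's mean by 0.01 × 1.8 = 0.018 to 0.01 × 3.4 = 0.034 points.
- If the arms differ by 1 to 3 percentage points and the credit is equal, the contrast moves by 0.018 to 0.03 × 3.4 = 0.102 points.
- SAP Appendix 3 puts the SD of WOMAC pain below 4. Dividing by 4 gives 0.0045 to 0.0255 SD; at an assumed SD of 3.5 the upper end is 0.102 / 3.5 = 0.029.

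*Cruder version.* Credit each such subject with the full arm mean. The shift in the contrast (MAR minus zero benefit) is fA × mA - fP × mP, where f is the share of the arm and m its mean change.

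| mA, mP | fA, fP | Shift |
|---|---|---|
| -5, -4 | 2%, 2% | -0.10 + 0.08 = -0.02 |
| -5, -4 | 5%, 5% | -0.25 + 0.20 = -0.05 |
| -5, -4 | 5%, 10% | -0.25 + 0.40 = +0.15 |
| -6, -5 | 10%, 5% | -0.60 + 0.25 = -0.35 |

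A negative shift means that MAR handling favours HP-5000. The sign depends on which arm has more such stops. The contrast is unchanged at equal rates only if the credit is also equal.

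**The case against.** **11.2.4 is narrow and not absolute.** It covers only adverse events whose treatment is a deviation, and the sponsor may let the subject continue. Both points stand. The section still does not send the site to 8.2.3, and its default is the opposite one.

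**The coding is less open than it looks.** Protocol 9.11 describes acetaminophen taken for target-knee pain as use prompted by lack of efficacy. SAP 16.1.5 counts non-compliance and protocol deviation as related. Protocol 8.2.3 requires every effort to establish an unknown reason. A reader might infer that a stop after NSAID use escapes the zero-benefit rule. The documents do not support that as a certainty: lack of efficacy is the natural code for uncontrolled knee pain, and an NSAID breach can be read as a related deviation. What stands is that no rule of priority exists and that the only entry naming prohibited medication lies in the unrelated group. Nothing cited requires the patch to be stopped after NSAID use, so the path may be uncommon. The MAR step is also a reading: it takes the 24-hour removal rule to cover permanent discontinuation, which the plan lists as a separate event.

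**Care.** A reader might infer that 7.2 promises care that the ban withholds. Staying is voluntary and the ban in 9.11 ends at early termination, so a deteriorating subject can stop, leave and return to standard care as 7.2 says. What remains is an observation: before Visit 8 that route means leaving the study, which works against the retention aim of 8.2.3.

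**Conclusion.** Two minor inconsistencies hold. First, 11.2.4 is out of step with the amended 8.2.3. Following it loses follow-up that matters for safety and for the supplementary and secondary analyses. A reader might extend this to the primary analysis, but that does not follow if scores more than 24 hours off patch are excluded. Second, the reason code for a patch stop after NSAID use for target-knee pain is ambiguous, and SAP 16.1.5 does not resolve it against the 8.2.3 list.

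The expected effect of the coding on the Week 12 contrast is small: at most about 0.03 SD in the conditional calculation. The cruder one reaches 0.35 points only with arm rates of 10% against 5%. Arm means, correlation and rates are all assumed, and the documents give none, so no claim of a large bias or a fixed direction is supported. The care question does not call for a required change.

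**What to change.** 1. **Protocol 11.2.4.** Replace withdrawal from the study with stopping study treatment if needed and continuing visits under 8.2.3, on the pattern of 11.2.7. Keep the subject-safety exception in 8.2.3, and record the reason and date of the stop.
2. **Protocol 8.2.3 and the eCRF guidelines.** State that a stop for target-knee pain needing a prohibited analgesic is coded as study treatment related, lack of efficacy. Reserve the prohibited-medication entry for use not caused by target-knee pain.
3. **Optional.** Note in 7.2 that before Visit 8 the return to standard care is through early termination.

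The cost is one sentence and one coding instruction. No new data are needed, because discontinuation reasons and concomitant medications are already collected.

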## 7.3. Study Sites

The study will take place at approximately [REDACTED] sites in the US that are qualified by background and experience and manage patients with OA. Each site is anticipated to screen a sufficient number of subjects to be able to randomize approximately [REDACTED] subjects, as detailed in the [Section 13.2](#).

## 8. SUBJECT POPULATION

### 8.1. Selection of Study Population

The study will enroll up to [REDACTED] subjects with pain of OA of the knee in a 1:1 ratio (HP-5000:Placebo). The pain should have been stable over the previous 6 months prior to Screening (Visit 1).

A screening log of potential study candidates and an enrollment log of enrolled subjects must be maintained at each study site, including reasons for screen failure.

### 8.2. Study Entry Criteria

All subjects being considered for participation in this clinical study must meet all the inclusion criteria and none of the exclusion criteria.

#### 8.2.1 Inclusion Criteria

A subject will be eligible for study participation if he or she meets all of the following criteria:

1. Provides written informed consent, prior to entering the study or undergoing any study procedures;
2. Male or female aged 40 to 85 years with a clinical diagnosis of OA of the target knee according to the American College of Rheumatology (ACR) criteria, including:
  - a. Symptoms for at least 6 months prior to Screening;
  - b. Pain in the target knee for 30 days of the preceding month (periarticular knee pain due to OA and not due to any other conditions such as bursitis, tendonitis, etc.);
  - c. The pain in the target knee required the use of NSAIDs either OTC per recommendation of a physician or by prescription (documented history is required).
  - d. On stable pain therapy (i.e., at least 3 days per week for the previous month) with an oral or topical NSAID prescribed or recommended by a clinician for 30 consecutive days prior to the Screening Visit.
3. Has an X-ray of the target knee, taken no more than 1 year before Baseline, showing evidence of OA with Kellgren-Lawrence grade 1 to 3 disease (as assessed by a radiologist).
4. Has pain of OA in the designated/target study knee:

[REDACTED]  
[REDACTED]  
[REDACTED]  
[REDACTED]  
[REDACTED]

[REDACTED]

[REDACTED]

[REDACTED]

6. Has a WOMAC pain score of [REDACTED] at the Baseline Visit (V3).

7. Able to swallow and tolerate rescue medication, APAP (moderately sized tablets).

8. Female subjects of non-childbearing potential (as defined as surgically sterile [i.e., history of hysterectomy or tubal ligation] or postmenopausal for more than 1 year [no menses for 12 consecutive months]), or if of childbearing potential must be non-pregnant at the time of Screening Visit and on the morning of Baseline Visit, and must agree to use hormonal or barrier birth control such as implants, injectables, combined oral contraceptives, some intrauterine devices (IUDs), sexual abstinence or a vasectomized partner during their study participation and for 90 days following the last dose administration. Transdermal contraceptives are not allowed. All female subjects must agree not donate blood during the study and for 90 days after completion of the study.

Male subjects who have not had a vasectomy must agree to use a barrier method of birth control example, either condom with spermicidal foam/gel/film/cream/suppository or partner with occlusive cap (diaphragm or cervical/vault caps) with spermicidal foam/gel/film/cream/suppository during their study participation and for 90 days following the last dose administration, and all male subjects must also not donate sperm or blood during the study and for 90 days after completion of the study.

9. Be reliable, willing, and able to cooperate with all study procedures including, but not limited to, the following:

- Accurately fill out the eDiary on a daily basis.
- Return for study visits on the required dates.
- Accurately and reliably report adverse symptoms (including treatment-emergent signs and symptoms) that he/she develops while participating in study.
- Use the patch as specified by the protocol.

### 8.2.2 Exclusion Criteria

A subject will be excluded from the study if the he or she meets any of the following criteria:

- Body mass index (BMI)  $> 40 \text{ kg/m}^2$  at Screening (Visit 1).
- The non-target knee pain severity score is [REDACTED] at Screening (Visit 1) and Baseline (Day 0).
- Any subject who did not follow the restriction of prohibited therapies during Washout period (including use of rescue medication within 3 calendar days prior to the Baseline Visit).

4. Arthritis of the target knee that is not caused by OA but caused by diseases such as rheumatoid arthritis, gout, psoriasis, syphilitic arthropathy, ochronosis, metabolic or other primary bone disease, or acute traumatic injury.
5. Any subject diagnosed with fibromyalgia.
6. Any other painful or disabling conditions affecting the target knee or leg.
7. Clinically significant elevation of serum creatinine ( $\geq 2$  mg/dL), aspartate aminotransferase (AST) or alanine aminotransferase (ALT) (at  $3 \times$  upper limit of normal [ULN]) at the Screening Visit.
8. Known allergy or hypersensitivity to diclofenac, APAP, acetylsalicylic acid (aspirin [ASA]), or any other NSAID, [REDACTED], glycerin, propylene glycol, or ethanol.
9. Severe uncontrolled cardiovascular, renal, hepatic, or other systemic illness/disease.
10. A documented gastroduodenal ulcer (by upper GI series or endoscopy), GI perforation or any GI bleeding (except hemorrhoidal bleeding) within 6 months prior to Screening Visit.
11. Documented history of alcohol or drug abuse within 1 year prior to study entry or positive alcohol/drug screen findings at Screening or Baseline.
12. Presence of chondrocalcinosis on X-ray if associated with a history of pseudogout or inflammatory flare-ups.
13. MAJOR SURGERY: Previous damage or surgery to the target knee at any time (i.e., damage/reconstruction of the anterior or posterior cruciate ligaments).
14. MINOR SURGERY on the target knee defined as anything other than major surgery (as defined above) within 1 year before study enrollment.
15. Treatment with oral or intra-muscular corticosteroids within 90 days of Screening Visit, treatment of the target knee with topical or intra-articular corticosteroids within 90 days of Screening Visit, or topical or intra-articular corticosteroid treatment of any other joint within 30 days of Screening Visit.
16. Any subject who had received intra-articular viscosupplementation (e.g., Synvisc®) in the target knee 90 days prior to Screening Visit.
17. Any subject who had received the following intra-articular drugs/biologics; anti-nerve growth factor agents, platelet rich plasma (PRP) injection, stem cells, prolotherapy and amniotic fluid injection in the target knee 6 months prior to Screening Visit.
18. Any opioid use 7 days prior to the Screening Visit.
19. Any subject who had previous exposure to HP-5000.
20. Any subject who needs to use cyclosporine, lithium, or methotrexate.
21. Use of another investigational drug or device within 30 days (or 90 days for biologics) prior to study entry.

22. Any subject with resolved, ongoing, or pending litigation or disability related to any health-related cause.
23. Any skin abnormality present at the potential patch application site (i.e., infection, rash, excessive fragility or dryness, any cut or abrasion or significant skin disorder such as atrophy, psoriasis, or vitiligo).
24. Any of the following skin conditions present at the potential patch application site; presence of tattoo, excessive hair or open sores, or scar tissue.
25. Any subject expecting to have knee replacement surgery within 6 months on the target knee or the non-target knee.
26. Any subject with a psychiatric condition that in the investigator's opinion may interfere with his/her participation in the study.
27. The subject is an employee, or family member of an employee, of the study center, the contract research organization (CRO) or the sponsor involved in this study.
28. Subjects who test positive for severe acute respiratory syndrome coronavirus 2 infection within 2 weeks prior to screening.

